### 11.4.3 Secondary Analyses

Repeated measures analysis of variance (MANOVA) 2

factors:

Factor 1: Intervention (intervention side vs. control side)

Factor 2: Time (baseline, 4th postoperative day and 6 weeks)

The significance level is set to  $p < 0.05$ . Statistical data analysis is carried out with SPSS.

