#### **Range of motion [degrees]**

To estimate the range of motion of knee flexion, the "RoMot" app from OT Bioelettronica (Turin, Italy) is used. The patient is in the supine position. The two sensors are applied to the lower and thigh legs. In response to the start command, the test subject tries to bend his knee as much as possible. The heel remains in bed and the longitudinal axis of the leg is also taken into account. Then the other side is measured. The number of degrees indicated by the software on the corresponding tablet is documented. Wireless Bluetooth sensors, for determining the amount of motion, show a high correlation compared to the goniometer measurements, which are currently the most commonly used in practice (Kumar et al. 2015). The measurement moments take place preoperatively, on the 4th postoperative day and 6 weeks postoperatively.

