#### **Skin temperature [°C]**

Skin temperature is also recorded with the help of an infrared thermometer (Voltcraft IR800-20D, Conrad Electronic, Hirschau, Germany). Handheld infrared thermal devices have high measurement accuracy (due to contact-free measurement) and practical handling (Stoop et al. 2020). Skin temperature is measured at four locations of the knee: superolateral, superomedial, inferolateral, and inferomedial margin of the patella (Zeng et al. 2016). The subject is in a supine position during the measurements. Both sides are measured. The measurement moments take place preoperatively, on the 4th postoperative day and 6 weeks postoperatively.

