## 7. CLINICAL INVESTIGATION POPULATION

### 7.1 Eligibility criteria

Subjects fulfilling all of the following inclusion criteria are eligible for the investigation:

- Signed Informed Consent by the participant

- Diagnosed gonarthrosis
- Planned implantation of a primary total knee endoprosthesis by the Regional Hospital Surselva AG

The presence of any one of the following exclusion criteria will lead to the exclusion of the subject:

- Decompensated hypertension in the affected area
- Acute inflammatory phlebitis in the affected area
- Patients with acute paroxysmal cold hemoglobinuria, or cryoglobulinemia
- significant vascular disorder in the affected area (e.g., due to previous frostbite, significant atherosclerosis, diabetes, or ischemic vascular disease)
- History of pulmonary embolism or risk factors for deep vein thrombosis or pulmonary embolism in the affected area
- Diseases such as active carcinomas or inflammation in the affected area, in which increased venous or lymphatic reflux is not desirable (as tumor cells and inflammatory parameters can be distributed throughout the body due to reflux)
- Severe or decompensated heart failure
- Raynaud's disease
- Hypersensitivity to cold
- Fear of cold/compression

The test subjects will be comprehensively informed about the process and possible risks before they are accepted to participate in the study. You will also receive the information in written form and have the opportunity to ask questions. The declaration of consent explains to them what their rights and obligations are when participating. In addition, they are informed that they may withdraw from participation at any time without giving reasons, without incurring any disadvantages as a result.

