## 7.3 Assignment to investigation groups

The group assignment is hidden with the help of a ticket in a sealed envelope, which is drawn under the supervision of the study director. This lot shows whether the subject is going through the Game Ready or Control intervention.

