### **8.1.2 Control Intervention (standard/routine/comparator)**

The test subjects receive standard physiotherapy, without Game Ready application. Standard physiotherapy after a total knee prosthesis includes the following interventions: The first physiotherapeutic treatment begins on the first postoperative day and consists of immediate loading of the operated leg (full weight bearing permitted according to the symptoms). Knee mobilisation with a passive movement machine and active knee mobilisation, instructed by the physiotherapist, are carried out. The treatment is carried out and documented by qualified and training physiotherapists at the Regional Hospital Surselva AG, [name]. The cooling applications with Game Ready do not conflict with standard therapy.

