### 11.4.2 Primary Analysis

The statistical data analysis will be carried out by [name] after completion of the data collection of the entire project.

Repeated measures analysis of variance (MANOVA) 2

factors:

Factor 1: Intervention (Game Ready vs. Control Intervention)

Factor 2: Time (baseline, 4th postoperative day and 6 weeks)

The significance level is set to  $p < 0.05$ . Statistical data analysis is carried out with SPSS.

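### The secondary analysis makes an undefined 'side' its Intervention factor and omits the randomised arm; read as operated versus other leg, the contrast is not randomised and mixes surgery with the device.

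*Combined protocol and SAP*

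**What the plan says.** Section 11.4.2 (primary analysis) sets up a repeated-measures analysis with two factors. The first is the randomised comparison, "Factor 1: Intervention (Game Ready vs. Control Intervention"; the second is time at three points. Section 11.4.3 (secondary analyses) repeats the model with the same time factor, "Factor 2: Time (baseline, 4th postoperative day and 6 weeks", and the same 0.05 level, but its first factor becomes "Factor 1: Intervention (intervention side vs. control side". The label *Intervention* is kept. Arm does not appear, and no arm-by-side term is given.

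The rest of the plan describes a parallel-group trial of patients. On allocation, section 7.3 says: "This lot shows whether the subject is going through the Game Ready or Control intervention". On the control group, section 8.1.2 says: "The test subjects receive standard physiotherapy, without Game Ready application". Section 7.1 requires one operation: "Planned implantation of a primary total knee endoprosthesis by the Regional Hospital Surselva AG".

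In the outcome descriptions, side means leg. For skin temperature section 5.1 says "Both sides are measured", with the same instruction for joint circumference; for range of motion it says "Then the other side is measured". Section 9.2.1 repeats all three. Sections 4.3 and 5.2 list no secondary objective or outcome, so nothing states what question 11.4.3 is meant to answer.

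**The concern.** A factor called *Intervention* should carry the randomised comparison. Here it carries a comparison that nobody randomised. No leg was allocated to control, and in control patients no leg receives the device, so neither level of the factor corresponds to an assigned treatment.

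If side means operated against other leg, surgery alone will separate the two levels after baseline, in both arms. Section 3.1 itself says that the operation promotes swelling and inflammation. A side effect, or a side-by-time effect, would then be reported under the heading *Intervention* although it is largely or wholly a consequence of the operation. The three outcomes concerned are collected on both legs at all three times, so the analysis can be run exactly as written. The trial aims to support treatment recommendations, and no text tells a reader to treat this analysis as descriptive.

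**Working it through.** The plan gives no figure for this contrast, so there is nothing to reproduce first. The check has three parts.

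**1. What the contrast estimates.** Let D be operated minus other leg, and ΔD its change from baseline to Day 4. Write s for the effect of surgery on the operated leg and d for the effect of the device. That the device goes on the operated leg is inferred; section 8.1.1 does not name the leg.

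- Game Ready patients: E[ΔD] = s + d
- Control patients: E[ΔD] = s
- All patients pooled, 1:1: E[ΔD] = s + d/2
- Difference between arms: (s + d) − s = d

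The side contrast contains s whichever patients are included. Only the between-arm difference isolates d.

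**2. Rejection rate of a Day 4 side test when d = 0.**

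Inputs: n = 14 per group (section 6.1) and α = 0.05 (section 11.4.3), taken as two-sided. Using Game Ready patients only is an assumption, because 11.4.3 does not name the population. The shift s and the SD of ΔD, written σ, are also assumed, in units of the outcome SD. For equal variances and separable correlations ρs (between legs) and ρt (between times), σ = 2√[(1 − ρs)(1 − ρt)]. Correlations of 0.5 and 0.5 give σ = 1.0. The range 0.89 to 1.41 corresponds to a product (1 − ρs)(1 − ρt) of about 0.2 to 0.5.

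Test: one-sample t on ΔD with 13 df, critical value 2.16, noncentrality λ = (s/σ)√14 = 3.742·s/σ.

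| s (SD) | λ at σ = 1.41 | Rejects | λ at σ = 0.89 | Rejects |
|---|---|---|---|---|
| 0.25 | 0.66 | 9% | 1.05 | 16% |
| 0.5 | 1.33 | 23% | 2.10 | 49% |
| 1.0 | 2.65 | 69% | 4.20 | 97% |
| 1.5 | 3.98 | 96% | 6.31 | 100% |

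**3. The three-time model as planned, against models that keep arm.** Simulation with 4,000 runs per row, 14 per arm, two legs, three times and both correlations 0.5. The operated leg shifts by s on Day 4 and s/2 at 6 weeks, and d = 0. Multivariate tests at 0.05. The Monte Carlo standard error near 5% is √(0.05 × 0.95/4000) ≈ 0.3 percentage points.

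| s (SD) | Side × time, all 28 | Side × time, 14 Game Ready | Arm × time, operated leg | Arm × side × time |
|---|---|---|---|---|
| 0 | 5.7% | 4.8% | 5.4% | 4.8% |
| 0.5 | 59.6% | 30.2% | 5.0% | 4.8% |
| 1.0 | 99.6% | 84.5% | 5.5% | 4.8% |
| 1.5 | 100% | 99.6% | 4.8% | 5.0% |
| 2.0 | 100% | 100% | 5.4% | 4.3% |

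The side test's error rate climbs with the surgery effect. The two tests that keep arm stay near 5%.

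**Masking.** Set s = +1 and d = −0.8 on Day 4, halved at 6 weeks. In Game Ready patients the net Day 4 shift is 1 − 0.8 = 0.2 SD, and the side-by-time test rejects in only 8% of runs although the device works. Arm × side × time rejects in 41%.

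**The case against.** **Side may not mean leg.** Section 11 never defines it, and the translation is visibly imperfect elsewhere: the abbreviation list renders ADE as a word of farewell. Side could be a loose word for arm, or leftover wording. A reader might infer that it can only mean operated against other leg; the documents do not go that far. Leg is the likelier reading, because that is how the outcome sections use the word and because with arm 11.4.3 would merely repeat 11.4.2. It remains an inference. That the factor is undefined is certain.

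**The bias need not favour the device.** A reader might infer that the analysis would credit the device with the effect of surgery. Section 11.1 hypothesises reductions in circumference and skin temperature, while surgery is expected to push at least the swelling the other way. A significant side effect would then more often look like harm or conceal a benefit. This objection stands. It changes the direction of the likely error, not the invalidity of the contrast.

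**The size is assumed.** A reader might infer a false-positive rate close to 1. That holds only for large surgery shifts; at 0.25 SD it is 9% to 16%. The rates are also two-sided, so they are not rates of false claims of benefit. This also stands.

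**The consequences are limited.** The primary analysis uses the randomised arm. No listed objective depends on 11.4.3, at most three outcomes are involved, and range of motion has no hypothesis in section 11.1. This limits the severity, but it does not make a test labelled *Intervention* interpretable when it omits the randomised intervention.

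**Conclusion.** The point holds in this form: 11.4.3 names an undefined side as its treatment factor and leaves out the randomised arm. On the most natural reading, a significant side or side-by-time effect carries no valid information about the device.

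With no device effect, the Day 4 side test in 14 patients rejects in roughly a quarter to a half of trials for a surgery shift of 0.5 SD, and in most or nearly all for 1 SD and above. These rates rest on the assumed shift, an SD of ΔD between 0.9 and 1.4, no dropout, and restriction to Game Ready patients. Under the simulation's assumptions, using all 28 patients makes the rates higher. That the contrast is confounded with surgery follows from the design and needs none of these numbers.

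The documents do not support saying that the device would be credited with a benefit, that leg is the only possible meaning, or that false rejection is nearly certain. The primary analysis is untouched. The plan should be corrected before analysis, since an undefined factor leaves its meaning to be chosen after the data are seen.

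**What to change.** Rewrite 11.4.3 as follows.

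- Define side, for example as operated leg against contralateral leg, and limit the analysis to circumference, range of motion and skin temperature.
- Keep randomised arm as the treatment factor. Test arm × side × time or, equivalently, arm × time on the operated-minus-contralateral difference. Changing the first factor to Game Ready against control without redefining the outcome in this way would only repeat 11.4.2.
- State which patients are included.
- Label any within-patient side comparison as descriptive, and not as evidence about the device.
- If side was meant as arm, delete 11.4.3 as a duplicate of 11.4.2.

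The cost is one paragraph of the plan. No new data are needed, because both legs are already measured at all three times.

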#### **11.4.4 Interim analyses**

The data is processed after the end of the respective subprotocol. Thus, the data analysis for the entire study takes place in stages. No additional interim analyses are planned.

#### **11.4.5 Deviation(s) from the original statistical plan**

Deviations from the planned statistical analysis are recorded and justified and reported to the CEC in the annual report.

### **11.5 Handling of missing data and drop-outs**

If a test subject does not complete the experiment, any data that has already been collected is retained, but is not further incorporated into the final data analysis.

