### **9.2.4 Assessment of safety outcomes**

No corresponding parameters are collected.

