## 10.3 Documentation and reporting in Medical Device Category A clinical investigations

Device deficiencies (DD) and all **adverse events (AE)** including all **serious adverse events (SAE)** are collected, fully investigated and documented in the source document and appropriate case report form (CRF) during the entire investigation period, i.e. from patient's informed consent until the last CIPspecific procedure, including a safety follow-up period.

- Documentation of AEs (including SAEs) by the PI includes diagnosis or symptoms, start and stop dates of event, event treatment, event resolution, assessment of seriousness and causal relationship to MD and/or investigation procedure (Art. 32 ClinO-MD, ISO14155).
- Documentation of DDs by the PI includes description of event, start date, investigational device information, action taken with regard to the investigational device, and whether the DD led to an AE. The Sponsor shall review all DDs and determine and document in writing whether they could have led to a SAE (DD with SADE potential) (Art 32. ClinO-MD, ISO14155).

The project works with a CE-certified product. It is a study with 30 or fewer subjects. The study focuses on basic findings. The study aims to gain fundamental knowledge in the field of cryotherapy in combination with compression. The monitoring for quality assurance is carried out by [name], PhD.

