#### **Reporting to the Competent Ethics Committee:**

The Sponsor reports to the CEC promptly any serious adverse event which has a causal relation with the MD, comparator or procedure/test method or where a causal relation appears to be possible (Art. 33 ClinO-MD).

In order to ensure prompt notification, the Sponsor may initially submit an incomplete notification.

If safety and health hazards that require measures must be taken immediately during the conduct of the investigation, the Sponsor notifies the CEC within 2 days of these measures and the circumstances which made them necessary (Art. 34 ClinO-MD).

Periodic safety reporting (Art. 35 ClinO-MD):

An Annual Safety Report (ASR) is submitted by the Sponsor to the CEC, yearly. The ASR contains a list of all SADEs and DDs and a report on their degree of seriousness, causal relationship with the MD and procedure and on subjects' safety.

Other reporting is done according to provisions of MD vigilance as per Art. 87-90 MDR (Art. 33 para. 4.b ClinO-MD) and Art. 67 MedDO.

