## 11.3 Statistical criteria of termination of the investigation

Only data from subjects who have completed the entire protocol will be included in the study. This ensures that all data has been collected under the same conditions and thus remains homogeneous and comparable.

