## 11.4 Planned Analyses

### 11.4.1 Datasets to be analysed, analysis populations

Only complete data sets will be included in the study. Data that contains only part of the protocol is not included in the analysis. No new subjects are being sought to replace the missing data.

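### Sections 11.3 to 11.5 exclude non-completers without excepting adverse events, and no adverse event summary is planned, so non-serious device effects that lead to withdrawal could be missing from the final results

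*Combined protocol and SAP*

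**What the plan says.** Three places in section 11 define who is analysed. Section 11.3: "Only data from subjects who have completed the entire protocol will be included in the study". Section 11.4.1: "Only complete data sets will be included in the study", and "Data that contains only part of the protocol is not included in the analysis". Section 11.5, on how participants who do not finish are treated in the final analysis: "If a test subject does not complete the experiment, any data that has already been collected is retained, but is not further incorporated into the" … None of them mentions adverse events, and no safety population is defined.

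On safety outcomes, 5.4 includes none. Section 9.2.4 says "No corresponding parameters are collected", and the adverse event subsection 9.2.4.1 holds only a dash. In contrast, 9.1 requires adverse events to be recorded at each visit. Section 10.3 says that device deficiencies and all adverse events "are collected, fully investigated and documented in the source document and appropriate case report form (CRF) during the entire investigation period", from consent through a safety follow-up.

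On reporting, 10.3.2 sends serious events, device deficiencies and hazards requiring action to the sponsor, and serious events with a possible or established causal link to the ethics committee. On the annual safety report it says "The ASR contains a list of all SADEs and DDs", together with a report on matters that include subjects' safety.

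Section 7.4 takes another line from section 11. When consent is revoked, what has already been collected has to enter the evaluation, on scientific and security grounds. It also returns the lot of a withdrawn participant and seeks a new one, whereas 11.4.1 rules out replacement.

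**The concern.** The exclusion can be triggered by the very event that a tolerability summary should count. Section 5.4 lets a participant who feels unwell stop and withdraw, and 8.2 allows removal on safety grounds, including feeling unwell. Section 10.3.1 lists local reactions during treatment, such as blisters, burning and discolouration. Only the device arm is exposed to them, so any loss falls mainly on that arm.

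The trial's stated purpose (3.1, 4.1) is to inform recommendations to therapists and physicians. A tolerability result limited to those who finished would be a weak basis for that.

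**Working it through.** The plan gives no safety figure to reproduce. The check follows one hypothetical patient through the text and then sizes the effect with assumed counts.

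**Tracing a device patient with a non-serious skin reaction who leaves because of it**

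1. Collection: recorded under 9.1 and 10.3, neither of which requires completion. Sections 9.2.4 and 9.2.4.1 say otherwise and need correcting.
2. Classification: under 10.2, a related event that meets no seriousness criterion is an adverse device effect (ADE). Section 10.3.1 introduces its list as serious, but 10.2 decides seriousness case by case, so a blister meeting no criterion is a non-serious ADE.
3. Reporting: 10.3.2 names serious events, serious device effects, device deficiencies and hazards requiring measures. A non-serious ADE is in none of these lists. The annual report's section on subjects' safety could mention it but is not told to. The content of the final report in 2.3.1 is not specified.
4. Analysis: 11.3, 11.4.1 and 11.5 leave the patient out. No adverse event table is planned for completers either.
5. Revoked consent: if the patient revokes consent, 7.4 requires the data to be evaluated and 11.5 excludes them. If the patient leaves or is removed under 8.2 without revoking consent, that rule in 7.4 does not apply and section 11 stands alone.

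**Size, by illustration**

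From the documents: 14 participants per group (6.1). Assumed: 1, 2 or 3 device patients leave because of a device effect, and nobody else in the arm, including any replacement, has one.

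The exact (Clopper-Pearson) 95% interval for x of n runs from the 0.025 quantile of Beta(x, n − x + 1) to the 0.975 quantile of Beta(x + 1, n − x). For x = 0 the lower limit is 0 and the upper limit is 1 − 0.025^(1/n). For example, 1 − 0.025^(1/11) = 28.5% and 1 − 0.025^(1/14) = 23.2%.

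| Leave for a device effect (assumed) | All randomised to the device | Completers, not replaced (11.4.1) | Completers, replaced (7.4) |
|---|---|---|---|
| 1 | 1/14 = 7.1% (0.2% to 33.9%) | 0/13 (0% to 24.7%) | 0/14 (0% to 23.2%) |
| 2 | 2/14 = 14.3% (1.8% to 42.8%) | 0/12 (0% to 26.5%) | 0/14 (0% to 23.2%) |
| 3 | 3/14 = 21.4% (4.7% to 50.8%) | 0/11 (0% to 28.5%) | 0/14 (0% to 23.2%) |

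The last two columns differ only because 7.4 and 11.4.1 disagree on replacement.

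**How likely is at least one such departure?** With true rate p per device patient, the probability among 14 is 1 − (1 − p)^14. That gives 25% at p = 2%, 51% at 5%, 77% at 10% and 96% at 20%. The documents give no rate, so these values of p are assumptions.

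**The case against.** The strongest reply is that section 11 concerns efficacy: its hypotheses and repeated-measures model contain no safety outcome, so there is no planned adverse event analysis for 11.5 to distort. Deleting 11.5 alone would produce no table. This stands. The gap comes as much from the missing safety summary as from the completers-only rule.

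A reader might infer that a harmed patient vanishes from the trial, or that the trial could report no device effects after seeing some. The documents do not support that. Section 10.3 documents events whether or not the participant finishes, and 10.3.1 follows up ongoing events after discontinuation. Section 9.2.5 records an injury that led to stopping and reports it to the sponsor. Under 10.3.2, serious device effects and device deficiencies reach the annual report. But collection and incident handling are not the same as a result by arm, and non-serious effects have no assigned place in one.

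Nor is it right that no text protects these data: 7.4 does so for revoked consent. For that route the fault is a contradiction rather than silence.

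Finally, stopping the device is not plainly the same as failing to complete. Section 5.4 separates ending the application from withdrawing, and the plan does not say whether someone who stops sessions but attends every visit has completed the protocol. The claim is therefore limited to participants who leave the study.

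**Conclusion.** The concern holds in this limited form. The plan excludes non-completers without excepting adverse events, plans no adverse event summary, contradicts 7.4 on data collected before consent is revoked, and contradicts itself on whether adverse events are collected. A non-serious device effect that led to leaving the study could therefore be absent from the final results, which would understate tolerability mainly in the device arm.

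The size cannot be fixed from the documents. In the largest case tabulated, an observed proportion of 21.4% becomes zero, and the upper confidence limit falls from 50.8% to 28.5%, or to 23.2% with replacement. This rests on assumed counts, on no events among the remaining patients, and on a completers-only table that the plan does not itself specify. The textual contradictions depend on none of these assumptions.

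**What to change.** - In 11.3, 11.4.1 and 11.5, limit the exclusion of non-completers to efficacy data.
- In 11.4.1, add a safety set of all randomised participants regardless of completion, with the device arm also shown for those who had at least one session.
- Plan one descriptive table by arm: number with any adverse event, any device effect, and withdrawal from the study or stopping of the device, with the reason where recorded.
- Reconcile 11.3 to 11.5 with 7.4 on data collected before consent is revoked, and 7.4 with 11.4.1 on replacement, because replacement changes the denominator.
- Make 9.2.4 and 9.2.4.1 refer to the collection in 10.3.

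The cost is a few sentences and one table, mostly from data that 10.3 already requires. The reason for stopping the device is not among the adverse event items listed in 10.3, so the data collection form may need one more line. Because 8.2 lets a participant revoke consent without justification, the reason will sometimes be missing and should be shown as such.
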